12.5 Secondary Analysis

12.5.1 Post-operative Pain Score

12.5.1.1 Analysis Population

Subjects will be grouped according to laterality of breast reconstruction (i.e., unilateral vs. bilateral). Within each group, experiment subjects will be compared to control subjects. Missing data will be dropped, and subjects who were non-adherent to the protocol will be excluded.

12.5.1.2 Analysis Plan

Data will be compared between the two groups using a two-tailed t-test.

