4.2 Hospitalization for reconstructive surgery

4.2.1 TAP Catheter Placement and Dosing:

On the day of surgery, bilateral TAP catheters will be placed using ultrasound guidance by the anesthesiologist in the pre-operative staging area prior to entering the operating room. Patients in the experimental group will receive an infusion of 0.125% bupivacaine and patients in the control group will receive an infusion of saline. Both groups will receive the following dosing:

- Initial bolus of 15mL pre-operatively
- 10mL bolus q4h intraoperatively with an option of 1-2mL per hour basal rate
- 10mL bolus q4h post-operatively with an option of 1-2mL per hour basal rate

TAP catheters will be discontinued on post-operative day (POD) 2, and the time will be recorded.

4.2.2 Post-Operative Pain Medication Regimen:

All patients will be provided with a patient controlled analgesia (PCA) infusion post-operatively providing IV hydromorphone. The PCA will be discontinued on POD2. Other pain medications available immediately after leaving the operating room will include the following:

- Acetaminophen IV or PO around the clock, per physician preference
- IV hydromorphone (dilaudid) 0.5 mg every 4 hours as needed for breakthrough pain, with an option to titrate up dose or frequency, per physician preference
- PO oxycodone 5-10 mg every 3 hours as needed for pain, with an option to titrate up dose or frequency, per physician preference
- Any pre-operative medications may be continued

4.2.3 Post-Operative Anti-Emetic Medication Regimen:

All patients will have available IV ondansetron (zofran) 4 mg every 4 hours as needed for nausea. Patients unable to take ondansetron will be given metocloprmiade (reglan).

4.2.4 Post-Operative Measurements:

Patients will be asked to rate their pain level on the Visual Analog Scale (VAS) every 4 hours while hospitalized unless they are sleeping. The total dosage of IV hydromorphone administered (via both the PCA and the as needed medications for breakthrough pain) will be recorded in 8-hour periods (midnight to 8am, 8am to 4pm, 4pm to midnight). The use of other pain medications, as well as anti-emetic medications, will be recorded in the same 8-hour periods. Time to ambulation, time to first bowel movement after surgery, and time to discharge will be recorded.

4.2.5 Evaluation for Discharge:

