9. STUDY CALENDAR

	Pre-Study	POD 0	POD 1	POD 2	POD 3-Discharge	1-6 months post-operatively
Investigational Treatment		X	X	X		
Informed consent	X					
Demographics	X					
Medical history	X					
Height	X					
Weight	X					
TAP catheter		X	X	X		
PCA		X	X	X		
Adverse event evaluation		X	X	X	X	
Evaluation for discharge ^a		X	X	X	X	
Pain evaluation	X	X	X	X	X	
BREAST-Q questionnaire	X					X

^aPatients will be evaluated daily for meeting discharge criteria and discharged when all criteria are met (detailed in Section 4.2.5).

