10.2 Secondary Outcome Measure: Post-operative Pain Score

10.2.1 Measurement Definition

Post-operative Pain Score is defined using Visual Analog Scale (VAS), a patient reported pain score on a scale of 0-10.

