10.2.3 Measurement Time Points

Post-operative Pain Score will be measured every 4 hours post-operatively unless the patient is sleeping.

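### The pain analysis applies a plain t-test to repeated 4-hourly scores without defining a value per patient or a time window, and leaves baseline pain unused

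*Combined protocol and SAP*

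**What the plan says.** All references are to the combined protocol and SAP.

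- **Endpoint (10.2.1):** "Post-operative Pain Score is defined using Visual Analog Scale (VAS), a patient reported pain score on a scale of 0-10". No mean, area under the curve, worst score or single time point is named.
- **Schedule (10.2.3):** "Post-operative Pain Score will be measured every 4 hours post-operatively unless the patient is sleeping". Section 4.2.4 adds the setting: "Patients will be asked to rate their pain level on the Visual Analog Scale (VAS) every 4 hours while hospitalized unless they are sleeping".
- **Calendar (section 9):** the row "Pain evaluation" is marked at Pre-Study, POD 0, POD 1, POD 2 and POD 3 to discharge.
- **End of the block (4.2.1):** "TAP catheters will be discontinued on post-operative day (POD) 2, and the time will be recorded".
- **Population (12.5.1.1):** patients are split by laterality. "Within each group, experiment subjects will be compared to control subjects". On incomplete data and non-compliance, the same section adds: "Missing data will be dropped, and subjects who were non-adherent to the protocol will be excluded".
- **Method (12.5.1.2), in full:** "Data will be compared between the two groups using a two-tailed t-test".

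The two drug-use outcomes are handled differently. Narcotic use (10.1) and anti-emetic use (10.3) are each a total per patient over 48 hours, and both are analysed by ANCOVA (12.4.2 and 12.5.2.2).

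**The concern.** A two-sample t-test assumes one independent value per patient. The pain outcome produces up to six readings a day per patient, running past catheter removal, and nothing says how they become one value or over which hours. The analyst must make that choice, and could make it after seeing the data. Some of the available choices are poor:

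- Pooling all readings treats repeated scores from one patient as independent. It also gives more weight to patients who stay longer or sleep less.
- A whole-stay mean mixes hours with the block and hours without it, over a window whose length differs between patients. Section 2.3 cites a retrospective review reporting shorter stays with the block. If that happened here, the averaging window would itself depend on treatment.

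Pain is the first-listed secondary objective (1.2.1). All patients have a PCA (4.2.2), so a difference in opioid use is hard to interpret without a sound pain comparison over the same hours.

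**Working it through.** **The plan's own figure.** The documents give no sample size or power figure for pain. The only one is for the primary outcome (12.6.2): difference 10 mg, SD 20 mg, 80% power, two-tailed t-test, 64 per arm. Alpha is not stated, and 0.05 is assumed here. The normal approximation gives n = 2 × (1.96 + 0.84)² × (20/10)² ≈ 62.7, so 63. The exact t calculation gives 63.77, so 64. The figure reproduces.

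**Inputs for pain.** From the documents: one reading per 4 hours, so at most 48/4 = 12 readings in 48 hours and 96/4 = 24 in 4 days, and catheter removal on POD 2. Not in the documents, and therefore assumed: within-patient correlation ρ of 0.3 to 0.7, the number of readings actually obtained, length of stay, and the correlation r between baseline and later pain.

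**Reading A: every score is a row.** Design effect DE = 1 + (m − 1)ρ. True two-sided error = 2 × [1 − Φ(1.96/√DE)].

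| Readings m | DE, ρ = 0.3 | Error | DE, ρ = 0.7 | Error |
|---|---|---|---|---|
| 8 (some lost to sleep) | 3.1 | 27% | 5.9 | 42% |
| 12 (48 hours, none lost) | 4.3 | 35% | 8.7 | 51% |
| 24 (4 days, none lost) | 7.9 | 49% | 17.1 | 64% |

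Simulation with 4,000 runs per setting agrees. At 64 per arm, m = 12 and ρ = 0.3, pooled rows reject a true null in 34.0% of runs and one mean per patient in 5.4%. At m = 24 and ρ = 0.5 the figures are 58.3% and 4.8%.

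**Reading B: one whole-stay mean per patient.** If the effect is confined to the first 48 hours, the fraction of the difference retained is 48 hours divided by the length of stay:

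- 3 days: 48/72 = 67%
- 4 days: 48/96 = 50%
- 5 days: 48/120 = 40%

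For an assumed effect of 0.5 SD on the 48-hour mean and 64 per arm, with ρ of 0.3 to 0.5, power falls from 80% to about 48%, 30% and 21%. Section 12.5.1.1 compares arms within laterality groups. With an assumed even split (32 per arm in each group), power for 0.5 SD is about 50% before any dilution.

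**Reading C: one 48-hour mean per patient.** Type I error is nominal, and there is no dilution from later days. The plan does not specify this reading.

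**Baseline pain, a separate matter.** Adjustment leaves a fraction 1 − r² of the variance: 1 − 0.09 = 0.91 at r = 0.3 and 1 − 0.25 = 0.75 at r = 0.5. Leaving it out therefore forgoes a variance reduction of 9% to 25%. In a randomized comparison this costs precision and does not bias the result.

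**The case against.** A reader might infer that the plan commits to testing every reading over the whole stay, so that the result must be either falsely precise or diluted. The documents do not support that.

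- Sections 4.2.4 and 10.2.3 describe when pain is collected, not what enters the test. Narcotic use is also recorded throughout the stay while its outcome is limited to 48 hours (10.1.3), so collection period and analysis window already differ in this protocol.
- Section 12.5.1.1 compares subjects, which points towards one value each and makes pooled rows the less natural reading.
- A 48-hour mean, one fixed time point, or a test at each time point fits the wording of 12.5.1.2 equally well and has neither defect, though the last raises multiplicity.
- Readings of 12 or 24 are maxima, because sleeping patients are not asked. Reading B assumes no effect after catheter removal. Section 2.2.3 says that blood levels become insignificant within three to six hours of a block injection, which makes fading plausible, but no section says that the effect stops.
- The pre-study pain evaluation is one calendar cell. Section 4.1 lists no pain score before surgery, and nothing says that this evaluation uses the 0-10 VAS.

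All of this stands, and it makes both error mechanisms conditional. It does not supply the missing definition: no section names a per-patient value, a window or a repeated-measures model for pain.

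**Conclusion.** The pain outcome is underspecified, and a plain t-test does not suit repeated readings. The size of the harm depends on a choice that the plan leaves open:

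- Pooled rows give a true type I error of about 35% to 51% with 12 readings, or 27% to 42% with 8, for an assumed ρ of 0.3 to 0.7.
- A whole-stay mean gives about half the difference for an assumed 4-day stay with no effect after 48 hours, over a window that varies with length of stay.
- A per-patient 48-hour mean gives neither problem.

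The documents do not show which of these would be run, so none of the figures predicts the trial's result. The unused baseline is a smaller point and concerns precision only. The issue is confined to a secondary outcome and should be settled before unblinding.

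**What to change.** In 10.2 and 12.5.1.2:

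1. Define one value per patient: the time-weighted mean VAS (area under the curve divided by time) over the first 48 hours. This is the primary outcome's window. It only approximates the block period, because catheters come out on POD 2 at a recorded time.
2. State how readings missed during sleep enter the calculation.
3. Compare arms by ANCOVA adjusting for the pre-study pain evaluation, provided that it is recorded on the same 0-10 VAS. Do this within laterality groups, as 12.5.1.1 states, or with laterality as a covariate if the strata are combined.
4. Report scores after 48 hours descriptively.

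A mixed model for the 0 to 48 hour scores with a patient random effect is an acceptable alternative, though it does not estimate exactly the same quantity when reading counts differ.

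**Cost.** The post-operative scores are already scheduled, so for them this is a wording change. The baseline term needs confirmation that the pre-study evaluation is a 0-10 VAS. If it is not, either that score is added before surgery or the covariate is dropped. The real loss is that pain after 48 hours is no longer formally tested.

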12.5.2 Post-operative Anti-emetic Usage

12.5.2.1 Analysis Population

Subjects will be grouped by study intervention, with experimental subjects being compared to control subjects. Missing data will be dropped, and subjects who were non-adherent to the protocol will be excluded.

12.5.2.2 Analysis Plan

Differences between the two arms will be evaluated using an analysis of covariance model. The comparison of the two arms will be made adjusting for the variables used in the stratified randomization.

12.5.3 Time to Ambulation

12.5.3.1 Analysis Population

Subjects will be grouped by study intervention, with experimental subjects being compared to control subjects. Missing data will be dropped, and subjects who were non-adherent to the protocol will be excluded.

12.5.3.2 Analysis Plan

Time to ambulation will be evaluated using a Cox proportional hazards model. The comparison of the two arms will be made adjusting for the variables used in the stratified randomization.

12.5.4 Time to First Bowel Movement

12.5.4.1 Analysis Population

Subjects will be grouped by study intervention, with experimental subjects being compared to control subjects. Missing data will be dropped, and subjects who were non-adherent to the protocol will be excluded.

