3.4 Randomization Procedures

Patients will be randomized within their surgery subtype (unilateral or bilateral) by the Stanford

Pharmacy to receive TAP catheters infusing either bupivacaine or saline. Randomization will occur using a computer software program to be implemented by the Pharmacy. The anesthetist placing the block, the surgeon performing the surgery, the nurses caring for the patient while hospitalized, and the research coordinators collecting data will be blinded to the randomization status.

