4.3 Post-operative follow-up (1-6 months post-operatively)

4.3.1 The post-operative BREAST-Q questionnaire¹⁹ will be administered at a clinic visit 1-6 months after surgery. If the study subject is unable to attend clinic in person during this time period, they will be asked to return the post-operative BREAST-Q questionnaire via email or fax. If the study subject does not return the post-operative BREAST-Q survey after 3 attempts by phone or email, the subject will be considered lost to follow-up and no further attempts will be made to have the patient complete the questionnaire.

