10.4.2 Measurement Methods

The time of first ambulation will be recorded by the nurse on shift. Time to Ambulation will be calculated from midnight on POD 1.

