10.5.2 Measurement Methods

The time of first bowel movement will be recorded by the nurse on shift. Time to First Bowel Movement will be calculated from midnight on POD 1.

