12.4.2. Analysis Plan

Differences between the two arms will be evaluated using an analysis of covariance model. The comparison of the two arms will be made adjusting for the variables used in the stratified randomization. The primary analysis will be a modified intent-to-treat principle (using recorded values where available regardless of compliance).

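### All five secondary analyses exclude non-adherent subjects, a post-randomisation condition the plan never defines, and no all-randomised version is planned

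*Combined protocol and SAP*

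**What the plan says.** The Analysis Population sections for pain (12.5.1.1), anti-emetic use (12.5.2.1), time to ambulation (12.5.3.1), time to first bowel movement (12.5.4.1) and quality of life (12.5.5.1) all contain the same sentence: "Missing data will be dropped, and subjects who were non-adherent to the protocol will be excluded".

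The primary analysis follows a different rule. Section 12.4.2 calls it modified intent-to-treat, "using recorded values where available regardless of compliance". Section 12.4.1 adds two extreme-value sensitivity analyses for missing data. The secondary outcomes have no sensitivity analysis and no version that keeps non-adherent subjects.

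No section says what makes a subject non-adherent, who decides, or when. Two places come near. Section 4.5 lists reasons for removal from the study, including a general discretion of the protocol director. Section 6 fixes the study infusion and rules out modifications. Neither is linked to the exclusion rule.

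On blinding, Section 3.4 covers the anesthetist, surgeon and nurses, and adds that "the research coordinators collecting data will be blinded to the randomization status".

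**The concern.** This is more than a missing detail. The plan states a rule that removes randomised patients because of something that happens after randomisation. If the reason is related to outcome, for example a catheter taken out early or a discretionary removal connected with pain or side effects, the patients left in each arm are no longer the groups that randomisation created. Because the term is undefined, two analysts with the same data could also build different populations.

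These analyses answer all five secondary objectives in Section 1.2. For each, the adherent-only result would be the only result.

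**Working it through.** **1. The rules side by side.** Both the primary and the secondary analyses rest on recorded values. They differ in the exclusion for non-adherence, and in the missing-data sensitivity analyses that only the primary has.

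**2. The plan's own figure.** Section 12.6.2 gives SD 20 mg, difference 10 mg, 80% power, a two-tailed t-test and 64 per arm. Alpha is not stated; two-sided 5% is assumed here and below. The standardised difference is 10/20 = 0.5. The exact t-test needs 63.77, rounded up to 64 per arm, with power 80.1%. The figure reproduces. It concerns the primary outcome and serves below only as a yardstick.

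**3. What has to be assumed.** The documents give no non-adherence rate and no SD for any secondary outcome. The exclusion fractions, the strength of selection and the pain SD below are all assumptions. Steps 4 and 5 use a t-test on a normal outcome at 64 per arm. Among the secondary outcomes that setting matches only quality of life (12.5.5.2), and unreturned questionnaires would lower the 64 further. It does not carry over to the Cox analyses of ambulation and bowel movement.

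**4. Exclusion unrelated to outcome.** With 5% or 15% lost per arm, 64 × 0.95 = 60.8 (61) and 64 × 0.85 = 54.4 (54) remain. There is no bias. Power at 0.5 SD goes from 80.1% to 78.2% and 73.1%. The difference detectable with 80% power goes from 0.499 SD to 0.511 and 0.544 SD.

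**5. Exclusion related to outcome, same blinded rule in both arms.** The outcome has SD 1, control mean 0 and treated mean -0.5 (lower is better). The odds of exclusion are multiplied by 2 or 4 per SD of worse outcome, with the intercept set so that 5% or 15% are excluded overall.

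| Excluded overall | Odds ratio per SD | Excluded, control / treated | Estimated effect | Shrinkage | Power |
|---|---|---|---|---|---|
| 5% | 2 | 5.8% / 4.2% | -0.489 | 2% | 77% to 78% |
| 5% | 4 | 6.4% / 3.6% | -0.468 | 6% | 76% |
| 15% | 2 | 17.1% / 12.9% | -0.474 | 5% | 71% |
| 15% | 4 | 18.5% / 11.5% | -0.430 | 14% | 66% to 67% |

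Shrinkage is 1 - |estimate|/0.5; for example 1 - 0.430/0.5 = 14%. Power is simulated with 20,000 trials per row, and a range shows the spread between repeat runs. With no true effect the same rule rejects in about 5% of trials.

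**6. Unequal exclusion, no true effect, pain score.** Section 12.5.1.1 compares arms within laterality and the group sizes are not given. An even split is assumed: 128/2 = 64 per laterality group, 32 per arm. Excluded patients are assumed to score 2 points worse than those kept, with SD 2 to 3 points.

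- Bias = 2 × (difference in excluded share). For 15% vs 5%: 2 × 0.10 = 0.2 points. For 15% vs 0%: 2 × 0.15 = 0.3 points.
- Standard error = SD × √(1/n₁ + 1/n₂). For 15% vs 5%, n = 27.2 and 30.4, giving 0.528 (SD 2) to 0.792 (SD 3). For 15% vs 0%, n = 27.2 and 32, giving 0.522 to 0.782.
- False rejection = Φ(-1.96 - bias/SE) + 1 - Φ(1.96 - bias/SE). For 15% vs 5% this is 6.7% (SD 2) to 5.7% (SD 3). For 15% vs 0% it is 8.9% to 6.7%.

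**7. The price of keeping everyone.** If non-adherent treated patients gained nothing at all, the effect would be 0.5 × (1 - f) = 0.475 at f = 5% and 0.425 at f = 15%, with power 76.0% and 66.5% at 64 per arm.

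**The case against.** The strongest reply is that the design leaves little room for outcome-driven exclusion. Staff and data collectors are blinded. Section 4.2.2 lets opioids be titrated up in dose or frequency, and Section 4.2.3 makes anti-emetics available as needed. The study infusion is fixed and the catheters come out on POD 2. A per-protocol analysis is also a legitimate tool, and in these illustrations a single blinded rule errs toward understating a real effect.

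Much of this stands. A reader might infer that patients needing more opioid would be excluded; the protocol does not support that, because titration is permitted care. No passage shows that outcome-related exclusion is likely, and the odds ratios of 2 and 4 are assumptions.

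A reader might also put 64 per arm into the pain comparison. The formula in step 6 would then give up to 8.3% (15% vs 5%) and 12.9% (15% vs 0%) false rejection. With 128 patients in total and comparison within laterality, that would leave the other laterality group empty, so those figures do not apply.

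The reply does not reach two things. Early catheter removal, or removal at the protocol director's discretion (Section 4.5), can still be related to pain or side effects, and blinding does not prevent that. And a per-protocol analysis is a sound supplement when its criteria are set in advance; here it has no criteria and stands alone.

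**Conclusion.** The point holds and should be fixed. It is confined to the secondary outcomes. A reader might infer that the primary result is compromised; it is not, because Section 12.4.2 does not use the exclusion.

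The plausible harm is modest. Under one blinded rule with 5% to 15% excluded, a 0.5 SD effect shrinks by about 2% to 14% with no excess of false positives. An excess needs the arms to lose different shares or kinds of patients; in the pain illustration it reaches 5.7% to 6.7%, or 6.7% to 8.9% in the more extreme case. All of these rest on assumed rates, selection strengths and SDs, and none is on the hazard-ratio scale.

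The case rests on keeping the randomised comparison and a population that can be reproduced. It does not rest on power: full dilution (step 7) could cost about as much as the selection in step 5.

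Censoring in the Cox models and the midnight POD 1 time origin are separate clarifications. A reader might take the sentence to mean that event-free patients are dropped from those models; the plan does not say so, and this point does not depend on it.

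**What to change.** In each of Sections 12.5.1.1 to 12.5.5.1, replace the quoted sentence with:

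> Subjects will be analysed in their assigned arm, "using recorded values where available regardless of compliance"; the number with missing values will be reported by arm. An analysis restricted to adherent subjects, with criteria fixed before unblinding, will be reported as a sensitivity analysis.

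The sponsor would still have to write the adherence criteria for the sensitivity analysis.

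The cost is SAP wording, with no new data. The downside is that effects may be diluted by non-adherence, as in the primary analysis. The change does not recover missing pain scores, or BREAST-Q forms from patients for whom, under Section 4.3.1, "the subject will be considered lost to follow-up".
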